#### 1.2 Existing knowledge

In the NHSBSP, each set of mammograms is read by two radiologists who each indicate if there should be a recall for further tests. Disagreements are referred for arbitration, usually by a third radiologist. Radiologists assess two mammograms per minute on average which equates to 120 in a 1-hour session. This is a highly skilled, pressurised but repetitive and frequently intellectually unchallenging activity. A vigilance decrement of performance decrease over time has been observed in similar repetitive visual tasks such as radar operator.

Data from an observational study using the Breast Screening Programme database for eight English breast screening centres for 3 years has shown that the probability of being recalled for further tests and of having cancer detected at screening is dependent on the time since the radiologist had a break from reading. For the first ten cases after a first reader break, the cancer detection rate for the whole process (including second reader and arbitration) is higher. These extra cancers detected are not associated with a higher probability of being DCIS rather than invasive, and have a similar mix of grades 1, 2 and 3 to the rest of the cancers detected at screening so this phenomenon is unlikely to be associated with increased overdiagnosis.

First and second readers read each batch of mammograms in the same order, thus their postbreak increases in cancer detection rate occur when reading the same women's mammograms.

## 1.3 Hypothesis

If the second radiologist examines the batch of mammograms in the reverse order to the first radiologist this will increase the overall cancer detection rates, because each radiologist's peak performance will be when examining different cases.

#### 1.4 Need for a Trial

A previous observational study has shown a reduction in sensitivity with a proxy for time (number of cases) since a break. Currently both radiologists are presented with cases in the same order as one another, so both have reduced sensitivity when reading the same cases. Therefore changing the order in which the second radiologist is presented with the mammograms may increase sensitivity of screening. A trial is required to determine whether such improvements would be realised in practice.

#### 1.5 Good Clinical Practice

The trial will be carried out in accordance with Good Clinical Practice (GCP) as detailed in the Medical Research Council (MRC) GCP guidelines (http://www.mrc.ac.uk/Utilities/Documentrecord/index.htm?d=MRC002416) and in accordance with the following protocol.

## 1.6 CONSORT

The trial will be reported in line with the CONSORT (Consolidated Standards of Reporting Trials) statement, and the further guidance available for cluster randomised controlled trials.

## 2 Trial Design

#### 2.1 Trial summary

The trial is a multi-centre cluster randomised parallel group superiority trial. The centres will be English Breast Screening centres with digital mammography equipment. The intervention is reversing the order in which the second radiologist reads each batch of mammograms. A cluster for randomisation is a batch of mammograms (circa 30 women's mammograms). The unit for analysis is the individual women's outcome.

The pre-pilot will be conducted in three screening centres for two weeks to ascertain the practical issues with implementation, and to test the Crystal report for data extraction. Concurrently a survey of all English breast screening centres will be conducted to ascertain key characteristics relevant to the trial which may differ between centres, such as the blinding of one reader to another's decision, and the method of arbitration used.

The trial will be implemented using an adaptation to the NBSS software used at participating centres.

The trial will last 16 months in 44 centres (1.5 million women). The first 12 months data (1.1 million women) will be collected from the NBSS database to determine whether the intervention affected cancer detection rate.

The full data set will be collected three years after the end of the study, to ascertain whether there was a decrease in rate of interval cancers (cancers presenting symptomatically in the three years after screening), and therefore whether the intervention reduced the number of cancers missed at screening.

## 3. Aims and Objectives of the Trial

## 3.1 Primary aim

To determine whether reversing the order in which the second reader reads the mammograms affects cancer detection rate.

## 3.2 Secondary aims

To investigate the mechanism by which the intervention is hypothesised to increase cancer detection rate. This is made up of several parts:

- 1. What effect does the intervention have on recall rate?
- 2. How well does the arbitration process perform?
- 3. Does reversing the order in which the second reader reads the mammograms increase disagreement between readers
- 4. Does cancer detection rate and recall rate change with time since a break?

To determine whether reversing the order in which the second reader reads the mammograms affects missed cancer rate.

#### 3.3 Outcome Measures

- a) Efficacy:
- i) Primary

Cancer detection rate in intervention and control group.

[figure not shown]
## ii) Secondary

- 1. Recall rate in intervention and control groups
- 2. Referral rate to arbitration, recall rate and cancer detection rate from arbitration, and positive predictive value of arbitration by type of arbitration used. Sensitivity and specificity of arbitration using 3 years follow up data
- 3. Disagreement rate in intervention and control group
- 4. Change in disagreement rate, recall rate, cancer detection rate, and missed cancer rate with intended reading order (and cases since a cancer, recall, and mid-batch break)
- 5. Rate of cancers detected symptomatically in the three years subsequent to screening in intervention and control group. To be collected three years after the trial implementation is complete. This provides a measure of the difference in rates of cancer missed.

iii) Health economicsCost per extra cancer detectedCost per quality adjusted life year gained from the intervention

## 2.2 Trial flow diagram

## CONSORT 2010 Flow Diagram for cancer detection analysis after 12 months

Trial Protocol CO-OPS Version 2 Page 6 of 11

## 3.4 Statistical Analysis Plan

## i) Primary

To determine whether cancer detection rate is higher in the intervention group in comparison to the control group analysis will be conducted using a multi-level logistic regression model.

Levels to be included in the model are case, batch, and centre. To prevent over-fitting each level will only be included if they explain a sufficient portion of the variability.

It is reasonable to expect characteristics at the level of the women screened to be very similar between intervention and control due to the large number of batches of women randomised. Similarly centre level characteristics such as the arbitration system used will not differ between intervention and control as randomisation is at the batch level within each centre. Therefore the main analysis will simply contain one predictor, intervention or control arm. The intervention will be considered effective if the 5th percentile of the distribution of the coefficient for the intervention in the model is greater than zero.

A second analysis will be conducted including adjustment for characteristics of the woman screened (age and whether they have previously attended screening). Sub-group analysis will be conducted in younger women, those whose cases are read at the beginning or end of the batch, and younger women, as the intervention may be more effective in these groups.

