## 4. Power and Sample Size

The trial is powered to detect at the 5% significance level with 80% power in a two tailed test a difference in cancer detection rate between intervention and control group of one extra cancer detected per 2000 women screened. This would correspond to around 1000 extra cancers detected by screening in England each year. Power calculations used cancer detection rate in the control group (7.8 per thousand women screened) and cancer detection rate in the intervention group (8.3 per thousand women screened). These estimates of cancer detection rate are derived from data from a previous study.

ICC was calculated from previous data, using a logistic binomial-Gaussian model (method B) with 1000 Monte Carlo simulations. [7] Hence, using the derived ICC of 0.002 and a cluster (batch) size of 40 women, this then gives the design effect as 1.09. This gave an overall sample size required of 1,093,780 women, or 44 breast screening centres for 1 year (On the basis that in England there are 82 centres each screening around 25,000 women per year).

Trial Protocol CO-OPS Version 2

There is no adjustment for drop out or crossover because once the intervention is applied to a screening centre each batch will automatically be randomly assigned to intervention or control groups by the NBSS computer system, and the intervention applied automatically by that same system. However, there is a possibility that a small minority of records (circa 5000) will not be updated in time for the data collection. These will be considered missing at random as they will be all the cases from certain dates. A further 2000 women may be recalled for further tests and not attend their appointment. Furthermore, some radiologists may not read cases in the intended order, for example coming back to re-read difficult cases at a later time. This also is expected to be very rare in a busy screening centre, (circa 2250 in intervention arm), these cases will be included in the analysis. Therefore 1,100,780 cases are required to be randomised, equivalent to 44 screening centres for 1 year.

The same method was applied to detect a difference in cancer detection rate between intervention and control group of one fewer cancer missed per 2500 women screened. This gave an overall sample size required of 1.5 million women, or 44 breast screening centres for 1 year and 4 months.

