#### Analysis 1:

The first model will include only treatment as a predictor of cancer detection. Levels considered for inclusion in the model will be: case; batch; and centre. To prevent over-fitting, each level will only be included in the final model if it explains a sufficient portion of the variability and improves model fit. Screening centre will be added as a level to the model to account for clustering. It will be retained in the model if it improves model fit (Wald test at the 5% level, see limitations section). Then batch will be considered for addition as a level to this model if it improves model fit according to the same criteria. The treatment will be added to this model.

A sub-analysis of those cases which are intended to be read in the first or last 5 of the batch, younger women  $(\le 52, 53-59, \ge 60)$  and the first batches to be read in a workday (by both readers) will be conducted.

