## Analysis 2:

The second model will adjust for other predictors of cancer detection in order to correct for any imbalances in these between intervention and control group.

First a model will be constructed with known predictors of cancer detection rate. The woman's age and whether she has previously attended screening are known to affect cancer detection rate and so will be included in the model as fixed effects. Then screening centre and batch will be tested for inclusion as levels in the model, using the same process as analysis 1. The treatment will be added to this baseline model.

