## Measures of variation

Table e2 shows random-effect (measures of variation) results from the multilevel analysis. In Model 1 (the empty model), there was a significant variation in the log odds of cancer detection across the batches ( $\tau$  = 0.811, 95% CI 0.757 – 0.866) and across the centres ( $\tau$  = 0.058, 95% CI 0.012 – 0.104). According to the intracentre and intra-batch correlation coefficient implied by the estimated intercept component variance, 1.4% and 20.9% of the variance of cancer detection could be linked to the centre- and batch-level factors, respectively. Variations across batches and centres remained statistically significant, even after controlling for treatment and background factors in the final model 4, thereby giving credence to the use of multilevel modelling to account for batch and centre variations.

The median odds ratio (MOR) results also confirmed the evidence of batch and centre contextual phenomena modifying the likelihood of cancer detection. In Models 1 and 2 the batch level heterogeneity is high (MOR of 2.35), but the centre level heterogeneity is low (MOR of 1.26). When the model is adjusted for age and whether the woman has been screened before (Models 3 and 4) the batch level MOR (2.08) remains high and the centre level MOR (1.20) remains low.

Table e2: Factors associated with cancer detection rate identified by multilevel multivariable logistic regression models.

Variable	Model 1 a	Model 2 b	Model 3 c	Model 4 d			
	OR (CI)	OR (CI)	OR (CI)	OR (CI)			
FIXED-EFFECTS (measures of association)							
Treatment variable							
Treatment (vs. control)		1.01(0.96-1.06)		1.01(0.97-1.06)			
Background factors							
Age (per year of age)			1.052(1.048-1.055)	1.052(1.048-1.055)			
No previous attendance			1.73(1.62-1.86)	1.73(1.62-1.86)			
RANDOM-EFFECTS (measures	s of variation)						
Centre level							
Variance (SE)	0.058(0.012-0.104)	0.058(0.012-0.104)	0.038(0.011-0.065)	0.038(0.011-0.064)			
Intra-centre correlation (%)	1.40	1.39	0.96	0.96			
MOR	1.26	1.26	1.20	1.20			
Wald statistics (p-value)	0.014	0.014	0.006	0.006			
Batch level							
Variance (SE)	0.811 (0.757-0.866)	0.809(0.754-0.863)	0.598(0.546-0.650)	0.595(0.543-0.647)			
Intra-batch correlation (%)	20.90	20.85	16.19	16.13			
MOR	2.35	2.35	2.08	2.08			
Wald statistics (p-value)	<0.001	<0.001	<0.001	<0.001			

<sup>aModel 1 is the empty model, a baseline model without any predictor variable

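### Choosing the treatment-only model as the main analysis on balance grounds overlooks precision; naming the already planned adjusted model as primary would be a modest, nearly free gain

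*Combined protocol and SAP*

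**What the plan says.** Protocol section 3.4 expects women's characteristics to be very similar between arms because so many batches are randomised, and centre characteristics not to differ because randomisation is within centre. It then states: "Therefore the main analysis will simply contain one predictor, intervention or control arm". An analysis adjusted for age and previous attendance is listed second.

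SAP section 6 keeps this order. For Analysis 1: "The first model will include only treatment as a predictor of cancer detection". For Analysis 2: "The second model will adjust for other predictors of cancer detection in order to correct for any imbalances". Analysis 2 fixes its two covariates in advance, age and previous attendance, on the ground that both are known to influence detection. SAP section 3 lists both among the items extracted for each woman. Neither document mentions precision as a reason for or against adjusting.

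Protocol section 4 gives the power target: "The trial is powered to detect at the 5% significance level with 80% power in a two tailed test", with detection rates of 7.8 and 8.3 per thousand, "using the derived ICC of 0.002 and a cluster (batch) size of 40 women".

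**The concern.** With randomisation by batch, the variance of the treatment effect has a between-batch part. Batches with more older women or more first attenders have higher detection rates. In a treatment-only model that predictable variation stays in the batch variance. Adjustment removes some of it, whether or not the arms are balanced. A balance argument therefore does not settle which model should be primary.

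The case did not need hindsight: the planners had both variables and already regarded them as prognostic. What is at stake is a small part of the precision of the primary comparison, in a trial sized at 80% power with an allowance of only about 7,000 women for missing records and non-attendance (1,100,780 − 1,093,780).

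**Working it through.** **Inputs.** Rates 0.0078 and 0.0083, two-sided 5%, 80% power, ICC 0.002, batch size m = 40 and total N = 1,093,780 (protocol section 4); m of about 30 as a sensitivity value (protocol section 2.1); batch variance on the log-odds scale 0.809 with treatment only and 0.595 after adjustment (Supplement 3, Table e2, Models 2 and 4).

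**1. The plan's own figure.** n per arm = [1.96·√(2p̄(1−p̄)) + 0.8416·√(p₁(1−p₁) + p₂(1−p₂))]² / (p₂−p₁)², with p̄ = 0.00805, gives 501,398 (SAP: 501,361). Multiplying by 2 × 1.09 gives about 1,093,050, against the stated 1,093,780. The formula 1 + 39 × 0.002 gives a design effect (DE) of 1.078, not 1.09, but the resulting 1,081,013 is within 3% of the stated total.

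**2. Share of batch variance explained.** 1 − 0.595/0.809 = 0.26.

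**3. Gain on the planning ICC.** Assume the batch component falls by the same proportion (factor 0.735).
- DE: 1.078 → 1 + 39 × 0.002 × 0.735 = 1.057.
- Required N: 1 − 1.057/1.078 = 1.9% lower.
- Standard error: 1 − √(1.057/1.078) = 1.0% lower.
- Power at N = 1,093,780, with N/(2·DE) effective women per arm: 80.5% → 81.2%.

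**4. Gain on the reported variances.** Each log-odds variance was converted to a proportion-scale ICC by integrating the logit-normal distribution at a mean rate of 0.0078. The ICC goes from 0.0091 to 0.0061.

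| m | DE, treatment only | DE, adjusted | Fall in SE | Power at 1,093,780 |
|---|---|---|---|---|
| 40 | 1.355 | 1.237 | 4.5% | 71.0% → 74.9% |
| 30 | 1.264 | 1.176 | 3.5% | 74.0% → 77.0% |

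In sample-size terms the difference is 2 × 501,398 × (1.355 − 1.237), about 118,000 women at m = 40, and about 88,000 at m = 30. A cruder conversion, p(e^variance − 1)/(1 − p), over rates of 7.8 to 8.3 per thousand and m of 30 to 40, gives a fall in SE of 3.9 to 5.2%.

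**5. Simulation check.** The design-effect route treats baseline risk as constant across batches once the covariates are in. A simulation without that simplification (25,000 batches of 40, total batch variance 0.809, of which 0.595 is left unexplained, cluster-robust logistic models, six replicates) gave a mean SE of 0.0262 unadjusted and 0.0255 adjusted, a fall of 2.4%. The range on the reported variances is therefore roughly 2 to 5%.

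**6. What the printed intervals show.**
- Cancer detection: 0.96-1.06 against 0.97-1.06. Log widths are 0.099 and 0.089, but two-decimal rounding allows a ratio from 0.72 to 1.11. This is uninformative.
- Recall (Table e3): ln(1.013/0.974) = 0.0393 and ln(1.016/0.978) = 0.0381, ratio 0.971 (rounding range 0.92 to 1.02).
- Disagreement (Table e4): ln(1.019/0.971) = 0.0483 and ln(1.020/0.974) = 0.0461, ratio 0.956 (rounding range 0.92 to 0.998).

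The secondary outcomes point the expected way, but only disagreement excludes no gain after rounding.

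**7. Individual-level gain.** With an assumed age SD of 5 to 7 years and 10 to 30% first screens, the odds ratios of 1.052 per year and 1.73 explain only about 0.1 to 0.2% of outcome variance, because the outcome is rare. Any useful gain comes through the batch variance.

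**The case against.** The size of the gain comes from the trial's own results. The SAP was agreed on 24/7/2013 and first data were collected on 23/10/2014, so the fall from 0.809 to 0.595 could not have been known. This stands as to size: on the planning inputs the gain is about 1% in standard error. It does not remove the argument, because the covariates were already known to be prognostic.

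The adjusted model is already pre-specified, with no selection among covariates, and the treatment-only model is valid under randomisation. This stands, and it makes the point one of ordering.

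A covariate-adjusted primary analysis could lose women. Below 5% missing data the SAP uses complete cases, so anyone without age or attendance status would drop out. The documents do not give that missingness. If it were 2 to 5% (an assumption), the loss would match or exceed the 1.9% sample-size gain on the planning ICC. This is a fair caution, although age and screening history are routine extract items.

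A reader might also infer more than the documents support:
- That the covariates explain most of the batch variance. They explain about a quarter; the reported intra-batch correlation stays at 16% and the batch median odds ratio at 2.08.
- That precision was given up for nothing. The plan gives a reason, and its model is simple and needs no covariate data.
- That the trial's conclusion depends on the choice. The treatment odds ratio is 1.01 in both models, and the supplement's text reports the adjusted one.
- That adjustment would restore the planned power. On the reported variances it stays below 80%; the excess of the observed clustering over the planning ICC is a separate and larger matter.

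**Conclusion.** The point holds as a modest efficiency improvement. The plan makes the less precise of two pre-specified models its main analysis, on a rationale that covers balance only. The cost is about 1% in standard error and under one power point on the planning ICC, and roughly 2 to 5% in standard error and three to four power points on the variances reported afterwards. The first figure assumes that the reported proportional fall in batch variance applies to the planning ICC. The power gain on the reported variances rests on the logit-normal conversion, a control rate of 7.8 per thousand and m of 30 to 40; the simulation suggests that it is towards the upper end. There is no bias or invalidity, and no sign that any conclusion would change.

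**What to change.** In protocol section 3.4 and SAP section 6, name Analysis 2 (treatment, age and previous attendance, with random intercepts for batch and centre) as the primary analysis, and report Analysis 1 as the unadjusted supportive analysis. Give precision as the reason for adjusting, in place of correcting imbalance. State how women with missing age or attendance status will be handled, so that they do not silently leave a complete-case primary analysis.

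The cost is a change of labels and a few sentences. Both models are already planned and both covariates already extracted; no extra women, data or modelling are needed.

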#### 2. Power and Sample Size

Currently, 14,700 cancers are detected by screening each year and the cancer detection rate is 7.8 per thousand women screened. (NHS Information Centre, 2012) To detect one extra cancer per 2000 women screened, this would increase the cancer detection rate to around 8.3 cancers per 1000 women screened. To detect this change of 0.5 cancers per 1000 women, for a two-tailed test at 80% power and 5% significance, 501,361 women are required in each arm, see figure 1.

However, as randomisation occurs at the batch level, collected data is clustered and must also be taken into consideration. The sample size of a clustered study must be increased by the Design Effect (DE), which is calculated as  $DE = 1 + (m - 1)\rho$  for a given ICC ( $\rho$ ) and cluster size (m).

ICC was calculated from previous data, using a logistic binomial-Gaussian model (method B) with 1000 Monte Carlo simulations. (Goldstein, 2002) Hence, using the derived ICC of 0.002 and a cluster (batch) size of 40 women, this then gives the DE as 1.09.

Therefore, the overall sample size required is for 1,093,780 women, or 44 breast screening centres for 1 year (On the basis that in England there are 82 centres each screening around 25,000 women per year).

There is no adjustment for drop out or crossover because once the intervention is applied to a screening centre each batch will automatically be randomly assigned to intervention or control groups by the NBSS computer system, and the intervention applied automatically by that same system. A woman could be lost to follow up if she is recalled from screening for further tests and does not attend her follow up appointment, however this is uncommon and so we have assumed low dropout rates for those who are recalled for further tests.

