#### 6. Statistical Analysis for primary outcome

To determine whether cancer detection rate is higher in the intervention group in comparison to the control group a two-tailed analysis will be conducted using a multi-level logistic regression model in Stata calling MLwiN software. MlwiN will be used because it can compute multi-level models for very large datasets without excessive computer hardware requirements.

Two models will be constructed as detailed below. For all models residuals will be examined for outliers. Analysis will be conducted as intention to treat, with all cases randomised included in the analysis. Missing data through loss to follow up will occur in both groups. This will include women who have been recalled from screening, but either did not attend their follow up appointment or there are no records in the database concerning the results of that appointment. Multiple imputation and sensitivity analysis to examine the effects of any missing data on the model will be considered if missing data is above 5% of the data set. Otherwise complete case analysis will be used.

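### The protocol's success rule for the primary outcome is in effect a one-sided 5% test, which contradicts the two-tailed 5% test behind the sample size and the two-tailed analysis in the SAP

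*Combined protocol and SAP*

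**What the plan says.** Protocol section 3.4 (i, Primary) frames the question in one direction: "To determine whether cancer detection rate is higher in the intervention group in comparison to the control group analysis will be conducted" with a multi-level logistic model. It then sets the decision rule. The intervention counts as effective if the 5th "percentile of the distribution of the coefficient for the intervention in the model is greater than zero".

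Protocol section 4 states a different standard: "The trial is powered to detect at the 5% significance level with 80% power in a two tailed test". SAP section 2 repeats it: "for a two-tailed test at 80% power and 5% significance, 501,361 women are required in each arm". SAP section 6 says that for the primary outcome "a two-tailed analysis will be conducted using a multi-level logistic regression model in Stata calling MLwiN software".

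The SAP neither repeats nor withdraws the 5th-percentile rule, and it has no sentence of its own saying when the intervention will be called effective. The 5% Wald criterion in SAP section 6 (Analysis 1) concerns whether centre and batch stay in the model as levels, not the treatment effect. Protocol section 8 and SAP section 1 both give 24 July 2013 as the date of agreement.

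**The concern.** A 5th percentile above zero means that the estimate exceeds 1.645 standard errors, which is the same as the lower limit of a two-sided 90% interval lying above zero. A two-tailed 5% test claims benefit only beyond 1.960 standard errors. The documents therefore hold two thresholds for one primary decision, and neither document justifies a one-sided rule or reconciles the two.

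A result in favour of reversed reading with a two-sided p-value between 0.05 and 0.10 would be declared effective under protocol section 3.4 and not significant under the SAP. Two analysts, each following a written document faithfully, could report opposite conclusions.

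The protocol rule is also silent on harm. The primary aim in protocol section 3.1 asks whether reversal affects detection, in either direction, but the rule does not say how a clear fall in detection would be declared.

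**Working it through.** **Inputs.** Control rate p1 = 0.0078 and intervention rate p2 = 0.0083 (protocol section 4); two-tailed 5%, 80% power and 501,361 women per arm (SAP section 2); design effect 1.09 and total 1,093,780 (both documents).

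**1. Reproduce the planned sample size.** With pooled variance under the null and no continuity correction:

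n per arm = [z_a √(2 p̄(1−p̄)) + z_b √(p1(1−p1) + p2(1−p2))]² / (p2−p1)²

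Here p̄ = 0.00805, 2p̄(1−p̄) = 0.015970, p1(1−p1) + p2(1−p2) = 0.015970 and z_b = 0.8416.

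| Test | z_a | n per arm | Against 501,361 |
|---|---|---|---|
| Two-tailed 5% | 1.960 | 501,398 | reproduces |
| One-sided 5% | 1.645 | 394,951 | does not (394,951/501,398 = 0.79) |

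Total: 2 × 501,361 × 1.09 = 1,092,967, against 1,093,780 stated, a difference below 0.1%. The trial was sized for a critical value of 1.960.

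**2. Chance of a false claim of benefit when there is no effect.**
- Two-tailed 5%: 1 − Φ(1.960) = 0.025 in the benefit direction, plus 0.025 in the direction of harm.
- 5th-percentile rule: 1 − Φ(1.645) = 0.050, all in the benefit direction.

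The ratio in the benefit direction is 2.0. The total is 0.05 in both cases.

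**3. Power at the planned size.**
- Effective number per arm: 1,093,780 / 2 / 1.09 = 501,734.
- Standard error of the difference: √(0.015970/501,734) = 0.0001784, or 0.178 per 1,000.
- Standardised effect: 0.0005/0.0001784 = 2.80.
- Two-tailed rule: Φ(2.80 − 1.96) = 80.0%.
- 5th-percentile rule: Φ(2.80 − 1.645) = 87.7%.

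The SAP's own formula gives a design effect of 1 + 39 × 0.002 = 1.078. Using that instead of 1.09 moves the two powers only to 80.5% and 88.0%.

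**4. Where the two rules disagree.** The thresholds are 1.645 × 0.1784 = 0.29 and 1.960 × 0.1784 = 0.35 extra cancers per 1,000. An observed gain between these would be effective under one document and not under the other.

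**5. The reported result** (Supplement 3, section B and Table e2).
- Adjusted: OR 1.01 (0.97 to 1.06). SE of log OR = [ln 1.06 − ln 0.97]/3.92 = 0.0226; z = ln 1.01/0.0226 = 0.44; two-sided p = 0.66, matching the reported 0.660. The 5th percentile of the OR is exp(0.00995 − 1.645 × 0.0226) = 0.97.
- Unadjusted: OR 1.01 (0.96 to 1.06). SE = 0.0253; 5th percentile of the OR = 0.97.

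On the log scale both 5th percentiles are below zero, so benefit is not claimed under either rule.

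**The case against.** The strongest reply is that the SAP is the dedicated analysis document, with log entries up to 23 October 2014. Its sections 2 and 6 together imply a two-tailed test at 5%, which is a usable threshold, and it does not carry the 5th-percentile sentence forward. The supplement then reports two-sided p-values and 95% intervals. On this view the SAP governed and nothing was inflated.

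Much of this stands. A reader might infer that the protocol sentence is the only criterion available; it is not, because the SAP's two sections supply one by implication. A reader might also infer that the false-benefit rate was in fact doubled; that follows only if the protocol sentence governs, and the reported analysis is two-sided. Nor does overall type I error double: only its benefit-side share does. The higher power under the protocol rule is not itself a harm.

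What the reply does not remove is the contradiction. No section gives the SAP precedence, and both documents were agreed on the same day. The SAP never states in words when the intervention is to be called effective, while the protocol does, with a different threshold. A pre-specified rule is judged by what it allowed before the results were known.

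**Conclusion.** The inconsistency is real and concerns the primary decision. Protocol section 3.4 sets a critical value of 1.645; the sample size and the SAP's two-tailed analysis imply 1.960. If the protocol rule were applied, the chance of a false claim of benefit would be 5.0% instead of 2.5%, with power of about 87.7% instead of 80% at the planned size.

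The practical effect is limited, because the reported conclusion is the same under both rules.

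These figures assume a normally distributed estimate and the planned rates and design effect. The protocol does not define the distribution of the coefficient. If it means a simulated posterior, the equivalence to a one-sided 5% test is approximate and assumes a flat prior.

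**What to change.** State one rule in both protocol section 3.4 and SAP section 6. Because results are already reported, do this as a dated clarification that names the section 3.4 sentence as inconsistent, and not as a silent replacement. Suggested text:

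*The intervention will be considered effective if the lower limit of the two-sided 95% interval for the treatment coefficient is above zero. An upper limit below zero will be reported as a reduction in cancer detection.*

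The cost is one short statement in each document. The sample size already matches this rule, and no data or reported estimates change.
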